2.3.1 Sample Size Estimates for Specific Aims

Hypothesis 1: The incidence of appropriate study observed GWG per week according to the 2009 Institute of Medicine guidelines¹ will be higher in the SmartMoms® group as compared to the Usual Care group.

The estimated incidences of appropriate GWG for the Usual Care group were derived from data based on pregnant individuals receiving WIC benefits in the 2013 Louisiana Pregnancy Risk Assessment Monitoring System.² The estimated effect size for the SmartMoms® intervention is based on preliminary data from our Expecting Success trial where the incidence of appropriate GWG for pregnant individuals with overweight was 12.3% for Usual Care versus 43.8% in SmartMoms®; and for pregnant individuals with obesity, 0% for Usual Care and 42.9% in SmartMoms®. However, since Expecting Success³ was not conducted in an exclusively underserved population, we conservatively estimated that the SmartMoms® intervention would increase the incidence by a minimum of 16% across BMI categories. The resulting overall incidence would be similar to our observation in Expecting Success (Table 1). To observe a 16% difference in the incidence between SmartMoms® and Usual Care while accounting for 15% attrition, at least 330 participants with 1:1 allocation between the two groups and equal stratification within each BMI stratum is required.

Table 1. Sample Size Estimates

BMI Category	Usual Care Appropriate GWG Incidence Rate	SmartMoms® Appropriate GWG Incidence Rate				
Normalweight	36.9	50.9	51.4	51.9	52.4	52.9
Overweight	23.9	37.9	38.4	38.9	39.4	39.9
Obesity	25.2	39.2	39.7	40.2	40.7	41.2
Overall	28.7	42.7	43.2	43.7	44.2	44.7
Sample Size		432	405	372	350	330

In additional to overall differences in incidence of appropriate GWG, this study is also powered to detect incidence differences within each BMI stratum. Assuming an overall difference in incidence of 16%, 110 participants in each BMI stratum are sufficient to detect a difference of at 26% in incidence within each BMI stratum (Table 2).

Table 2. Power For Detecting Differences Within Each BMI Stratum

Difference in Incidence	Power
23%	0.70
26%	0.80
29%	0.88

Hypothesis 2: Study observed GWG seen in the SmartMoms® group will be less as compared to the Usual Care group. This will be assessed using the following three measures: study-observed GWG, weekly GWG, and deviation from the 2009 Institute of Medicine guidelines.¹

We will investigate study observed GWG, weekly GWG, and deviation between the observed rates of weekly GWG and rates deemed appropriate by the 2009 IOM. Based on our pilot data (Table 3), pregnant individuals with overweight and obesity in the SmartMoms® group had comparable deviation rates (gaining an additional ~0.06 kg/week above the recommended amount) whereas the Usual Care group had a greater deviation rate that was seen in both BMI strata. With our planned sample size of at least 330 participants, we have more than 80% power to detect a difference of at least 0.16 kg/week between the SmartMoms® and Usual Care group and within each BMI category, and over 99% power to show overall differences between groups in study observed GWG.

Table 3. Weekly GWG in Expecting Success

BMI Category	Usual Care Weekly GWG Deviation Rate (kg/week)	SmartMoms® Weekly GWG Deviation Rate (kg/week)
Overweight	0.208	0.063

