1.4 Subgroups

Per the 2009 Institute of Medicine guidelines, each BMI category is allocated a different rate of GWG per week [1]. Therefore, intervention effects within each body mass index (BMI) category (normal weight, overweight, obesity) will be determined as a subgroup analysis. The study sample sizes are powered to detect differences within each subgroup.

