2.3 Sample Size and Study Power

Study hypotheses will be assessed using appropriate statistical tests, input variables and endpoints, and therefore, power calculations and sample size estimates are presented for the study aims. Estimates of the study power are derived from our preliminary data and from existing literature. The 1:1 randomization scheme within each BMI stratum is applied to ensure that the study is also sufficiently powered to compare intervention effectiveness within BMI groups which is important for the program announcement (PA-18-135).

The sample size estimates assume β =0.8 and α =0.05 to detect the specified differences between incidence rates of appropriate GWG. All sample sizes are inflated to account for 15% attrition. Intent-to-treat (ITT) analyses will be used. Participants are required to have at least one follow-up clinic weight to compute GWG (incidence rate, study observed, per week, and deviation). We plan to enrol at least 330 participants, with relative balance within each BMI stratum. We have sufficient power for our primary comparisons of GWG as well as comparisons within BMI groups. Due to the Covid-19 pandemic impacting trial procedures and enrolment, the goal of this study is to enrol at least 330 participants. That is, the study will continue to enrol individuals until either the end of the enrolment period (December 2023, with participants having to be certified to receive WIC benefits by October 31, 2023, to be eligible) or until all three BMI categories have 110 enrolled participants. Enrolment in any given BMI category will continue past 110 if the other BMI categories have yet to meet the enrolment goal.

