3.4 Missing data

No statistical imputation of missing values will be conducted (data as observed) per contemporary guidelines.⁴

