4 ANALYSIS

4.1 Analysis Populations

Analyses will rely on ITT methodology. The primary analysis will use data from the visits during early and late pregnancy. For participants that had missing data at the late pregnancy time point, we will conduct a sensitivity analysis in which we use data from the visit during mid-pregnancy to calculate outcomes related to GWG per week for these individuals; that is, the incidence of appropriate study observed GWG per week according to the 2009 Institute of Medicine guidelines, as well as weekly GWG and deviation from the 2009 Institute of Medicine guidelines.¹

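### SAP Table 2 overstates power within BMI categories: it treats all 110 enrolled per category as analysed, so 80% power at 26 points becomes about 73% after the plan's own 15% attrition

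*SAP*

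**What the plan says.** SAP 2.3 sets a general rule: "All sample sizes are inflated to account for 15% attrition". It then describes enrolment as continuing to the end of the enrolment period or "until all three BMI categories have 110 enrolled participants", so 110 per category is a count before losses. SAP 2.3.1 applies the allowance explicitly to the overall comparison ("while accounting for 15% attrition, at least 330 participants with 1:1 allocation between the two groups").

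For the BMI categories, the same section states that "110 participants in each BMI stratum are sufficient to detect a difference of at 26% in incidence within each BMI stratum". Table 2 gives power of 0.70 at 23 points, 0.80 at 26 and 0.88 at 29. Neither the sentence nor the table mentions attrition, the Usual Care rate or the test.

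Two further statements rest on these figures. SAP 1.4 says: "The study sample sizes are powered to detect differences within each subgroup". SAP 2.3 says: "We have sufficient power for our primary comparisons of GWG as well as comparisons within BMI groups".

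**The concern.** The two tables in SAP 2.3.1 appear to use different bases. If Table 1 counts only those expected to remain after losses and Table 2 counts everyone enrolled, the subgroup power is overstated relative to the SAP's own rule.

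The allowance matters because losses do reduce the number analysed. SAP 3.4 says "No statistical imputation of missing values will be conducted (data as observed", and SAP 4.1 says "The primary analysis will use data from the visits during early and late pregnancy". A participant without a late-pregnancy weight therefore contributes nothing to the primary incidence comparison.

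The stake is interpretation. SAP 2.3 ties within-BMI power to the funder's program announcement, and SAP 4.3 commits to reporting results within each BMI category. A reader of Table 2 would take a non-significant category result as coming from a comparison with 80% power at 26 points.

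**Working it through.** **Inputs.** Two-sided α = 0.05 and 80% power (SAP 2.3 writes β = 0.8 and does not state sidedness; one-sided calculations do not reproduce the tables). Allocation 1:1 (SAP 2.2). Attrition 15% (SAP 2.3). Usual Care rates from Table 1: 28.7% overall, 36.9% normal weight, 23.9% overweight, 25.2% obesity. Enrolled per category: 110, so 55 per arm, or 110 × 0.85 / 2 = 46.75 per arm after attrition.

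**Formula** (pooled variance under the null, n per arm, d = p2 − p1, p̄ the mean of p1 and p2):

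power = Φ{ [d − 1.96 √(2p̄(1 − p̄)/n)] / √([p1(1 − p1) + p2(1 − p2)]/n) }

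**Step 1: Table 1, p1 = 0.287.** The method gives the SAP's 80% only after attrition is taken off.

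| Difference (points) | Enrolled | Per arm after 15% | Power after 15% | Power, no attrition |
|---|---|---|---|---|
| 14 | 432 | 183.6 | 0.802 | 0.862 |
| 14.5 | 405 | 172.1 | 0.803 | 0.863 |
| 15 | 372 | 158.1 | 0.795 | 0.856 |
| 15.5 | 350 | 148.75 | 0.796 | 0.857 |
| 16 | 330 | 140.25 | 0.797 | 0.858 |

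**Step 2: Table 2, same method and control rate.** At 26 points, p2 = 0.547 and p̄ = 0.417.

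- 55 per arm: standard errors 0.0940 (null) and 0.0907 (alternative); (0.26 − 1.96 × 0.0940)/0.0907 = 0.835; power 0.798.
- 46.75 per arm: standard errors 0.1020 and 0.0984; (0.26 − 1.96 × 0.1020)/0.0984 = 0.611; power 0.729.

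| Difference (points) | Table 2 | 55 per arm | 46.75 per arm |
|---|---|---|---|
| 23 | 0.70 | 0.697 | 0.624 |
| 26 | 0.80 | 0.798 | 0.729 |
| 29 | 0.88 | 0.877 | 0.819 |

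**Step 3: what n does Table 2 imply?** Solving for n from the rounded powers gives 54.8–56.1, 54.6–55.9 and 54.6–56.4 per arm. The common range is 54.8–55.9, which contains 55. Repeating this for all four Table 1 rates gives 52.1–58.3 per arm pooled and 49.5–55.8 unpooled. All of these exceed 46.75.

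**Step 4: sensitivity at 26 points, 46.75 per arm.**

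| Usual Care rate | Pooled | Unpooled |
|---|---|---|
| 28.7% | 0.729 | 0.753 |
| 36.9% | 0.717 | 0.740 |
| 23.9% | 0.749 | 0.772 |
| 25.2% | 0.742 | 0.766 |

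The arcsine method at 28.7% gives 0.733. Reading the allowance as 110/1.15 instead gives 0.739. A continuity-corrected or Fisher exact test gives about 0.64–0.68, so the shortfall would be larger under those tests.

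**Step 5: what the design delivers.** With 46.75 per arm, the difference detectable at 80% power is 28.3 points at the 28.7% rate. Over the three category rates it is 27.7–28.6 pooled and 26.9–27.8 unpooled. Keeping 80% at 26 points needs 55.26 analysed per arm, or 2 × 55.26 / 0.85 = 130 enrolled per category. If the 339 to 360 projected in the SAP's amendment to Section 2.1 were split equally (an assumption), 113 to 120 per category would give 0.74 to 0.77.

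**The case against.** The strongest objection is that Table 2 names no control rate, test or analysed number, so the omission of attrition is inferred. A calculation after attrition can give the same figures: unpooled, 46.75 per arm and a 19% Usual Care rate yield 0.703, 0.801 and 0.877. That stands as a reason to call this a reconstruction. It does not rescue the table, because no document gives a 19% rate. Reaching 0.80 at 26 points after attrition needs a rate of 16.1% (pooled) or 19.2% (unpooled), below every rate in Table 1. The pilot Usual Care rate of 12.3% for overweight gives 0.84 pooled or 0.86 unpooled at 26 points, but it does not reproduce Table 2, and SAP 2.3.1 says the Usual Care rates come from the state surveillance data.

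The Table 2 sentence also begins from an overall difference of 16 points, which a single-stratum calculation does not use, and the parallel sentence in Protocol 12.2 concerns differences between BMI groups. The role of the 16 points is unexplained. However, the SAP sentence is explicitly about differences within each stratum, and the plain two-proportion calculation matches all three entries.

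On losses, SAP 2.3 asks for at least one follow-up weight, and SAP 4.1 uses mid-pregnancy weights in a sensitivity analysis, so actual losses may differ from 15%. A category may also exceed 110. Neither point changes what Table 2 should show for 110 enrolled under the SAP's own allowance.

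Finally, the practical effect is modest. The SAP is dated May 2024, after the planned end of enrolment, and results will be reported as effect estimates. At the 16-point planning difference, category power is only 34–38% after attrition and 39–44% without it, so the categories are weakly powered for that effect either way. This limits the importance of the error but does not make the stated 0.80 correct.

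**Conclusion.** The concern holds. On the SAP's attrition rule, 110 enrolled per BMI category gives power of about 0.62, 0.73 and 0.82 at 23, 26 and 29 points, against the stated 0.70, 0.80 and 0.88. At 26 points the range is 0.72–0.77 across the Table 1 control rates and the pooled and unpooled tests. The detectable difference at 80% power is about 28 points (26.9–28.6 over the same choices), not 26.

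This assumes a two-sided 5% test, equal arms, exactly 110 enrolled per category, 15% loss in each arm and Usual Care rates as in Table 1. The error is confined to the stated subgroup power. The overall primary comparison carries the attrition allowance correctly.

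**What to change.** Restate Table 2 on evaluable numbers: about 0.62, 0.73 and 0.82 for 110 enrolled, or figures for the numbers actually evaluable in each category. Alternatively, give the within-category detectable difference as about 28 points (27–29 across tests and control rates). The study statistician should state the Usual Care rate, the test and the analysed number behind the table, and either explain or drop the reference to a 16-point overall difference. The subgroup-power sentences in SAP 1.4 and 2.3 should then refer to the corrected difference.

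The cost is one three-row table and a few sentences. The stated subgroup power becomes less favourable. No participants are added and no analysis changes.

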12.2. Sample Size Consideration

To observe a 14% increase in the incidence rate of GWG (**Hypothesis A**), and accounting for 15% attrition, a total of 432 participants with 1:1 allocation between the two groups (SmartMoms[®] and Usual Care) and equal stratification across the three BMI categories (n=144) is required to detect a significant difference. The sample size estimates assume β =0.8 and α =0.05 to detect the specified increases in the incidence rate of appropriate GWG. The incidence rates of appropriate GWG for the Usual Care group were derived from women receiving WIC benefits in the 2013 Louisiana Pregnancy Risk Assessment Monitoring System data (95). The estimated effect size is based on our pilot trial data where the incidence rate of appropriate GWG for Usual Care versus 43.8% in SmartMoms[®]; and for obese women 0% for Usual Care and 42.9% in SmartMoms[®]. However since the pilot trial was not in an exclusive under-served population, we conservatively estimate that the SmartMoms[®] intervention will increase the incidence rate by a minimum of 14% across each BMI category.

This study is also powered to detect BMI group changes in incidence rates. Assuming an overall average change in incidence rate of 14%, 125 participants in each BMI group (accounting for 15% attrition) is sufficient to detect an incidence rate that is at least 20% different between BMI groups.

In addition, we will also investigate the rate of GWG per week (**Hypothesis B**). Per the 2009 IOM guidelines, each BMI category is allocated a different rate of GWG per week (79). We will investigate the deviation between the observed rates of GWG and rates deemed appropriate by the 2009 IOM. Our pilot data from the 'Expecting Success' study showed that both overweight and obese women in the SmartMoms[®] gained an additional 0.06 kg/week above the recommended amount, which was approximately 3 times higher in the Usual Care groups (0.21 and 0.16 kg/week for overweight and obese women respectively). With our planned sample size of 432 participants, we have more than 80% power to detect change a change as small as 0.12 kg/week between SmartMoms[®] and Usual Care and within each BMI category and over 99% power to show overall differences in rates of weekly GWG.

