The sample size was updated to a minimum of 330. The initial estimated effect size for the SmartMoms® intervention was based on preliminary data in the Expecting Success trial. The incidence of appropriate GWG for people with overweight was 12.3% for Usual Care versus 43.8% in SmartMoms®, and in people with obesity, it was 0% for Usual Care and 42.9% in SmartMoms®. However, the Expecting Success trial was not conducted in an exclusively underserved population, so we needed to conservatively estimate the SmartMoms® intervention effect to ensure this study would be well powered. The incidence of appropriate GWG for the Usual Care group was derived from individuals receiving WIC benefits in the 2013 Louisiana Pregnancy Risk Assessment Monitoring System data. The table below was created to show the incidences needed for 80% power in each of the BMI categories. All the estimates were tenable since they were lower than the SmartMoms® trial estimates. This study aimed for a total sample of 432 originally to allow for unknown variability that may have caused the observed rates to be different than the ones used for the power analysis. Sample size was reassessed in response to the COVID-19 pandemic. Based on the feasible recruitment estimates, the sample size was lowered to a minimum of 330. No new data were used to obtain the changes in power.

Table 1. Sample Size Estimates

BMI Category	Usual Care Appropriate GWG Incidence Rate	SmartMoms® Appropriate GWG Incidence Rate				
Normalweight	36.9	50.9	51.4	51.9	52.4	52.9
Overweight	23.9	37.9	38.4	38.9	39.4	39.9
Obesity	25.2	39.2	39.7	40.2	40.7	41.2
Overall	28.7	42.7	43.2	43.7	44.2	44.7
Sample Size		432	405	372	350	330

Section 3.0

Amendment May 2024:

Section was rewritten to clarify that treatment group differences within each BMI category is an apriori subgroup analysis we would consider.

Section 3.1

Amendment May 2024:

Description of methodology used to assess distributional assumptions was reduced to allow for which test is most statistically appropriate to be used.

Section 3.3

Amendment May 2024:

Based on recommendation from other statistical analysis experts in maternal health, a priori variable selection for determining covariates will be used. Gestational age at randomization, BMI category at randomization, and categorically defined parity will be the only covariates to be included in the model. Exploratory analysis will examine relationships of the outcomes with other

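### The SAP describes Hypothesis 2 as adequately powered within BMI groups, but its detectable difference of 0.16 kg/week exceeds both pilot differences (0.145 and 0.10) and is not the protocol's 0.12 rescaled to N=330

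*SAP*

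**What the plan says.** SAP 2.3 says that its power estimates come from preliminary data and existing literature, that all sample sizes allow for 15% attrition, and that power is adequate for the primary GWG comparisons and for comparisons within BMI groups. SAP 1.4 says that the sample sizes are powered for differences within each BMI subgroup.

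For Hypothesis 2, SAP 2.3.1 cites the pilot deviations from the IOM weekly rate and then states, for a sample of 330 or more, "we have more than 80% power to detect a difference of at least 0.16 kg/week between the SmartMoms® and Usual Care group". The sentence covers each BMI category as well, and it adds "over 99% power to show overall differences between groups in study observed GWG". No standard deviation is given, and no difference is attached to the 99% statement.

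Protocol 12.2 puts the pilot excess at 0.06 kg/week in SmartMoms, and as "approximately 3 times higher in the Usual Care groups (0.21 and 0.16 kg/week for overweight and obese women respectively"). With 432 participants it claims more than 80% "power to detect change a change as small as 0.12 kg/week", also within each BMI category. It gives no standard deviation either.

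The SAP amendment log, in its entry for Section 2.3, attributes the smaller sample to recruitment after COVID-19 and says "No new data were used to obtain the changes in power".

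**The concern.** A detectable difference supports a claim of adequate power only if it is no larger than the effect the trial expects. The only expected effect that the documents give for Hypothesis 2 is the pilot difference. The protocol's 0.12 lay below the overweight pilot difference; the SAP's 0.16 lies above both. The SAP therefore shows 80% power in neither of the two strata with pilot data, while describing within-BMI power as adequate.

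The change from 0.12 to 0.16 is also larger than the cut in sample size explains, and no other reason is given.

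SAP 4.3 says that the Hypothesis 2 analyses will be reported within each BMI category. A null result in obesity, read beside a statement of adequate power, could be taken as evidence of no effect when the chance of detecting the pilot effect may have been about one half or less.

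**Working it through.** **Inputs**

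- Alpha and power, SAP 2.3: "The sample size estimates assume β =0.8 and α =0.05". The 0.8 is read as power. Sidedness is not stated; two-sided is assumed.
- SAP: N=330, 110 per stratum, 55 per arm per stratum. After 15% attrition: 55 × 0.85 = 46.75 per arm per stratum, and 3 × 46.75 = 140.25 per arm overall.
- Protocol: N=432, 144 per stratum, 72 per arm per stratum; 72 × 0.85 = 61.2 after attrition.
- Pilot differences: overweight 0.208 - 0.063 = 0.145 (SAP Table 3); obesity 0.16 - 0.06 = 0.10 (protocol 12.2). The documents give no pilot figure for normal weight.
- Assumption: the pilot difference in deviation equals the difference in weekly gain.

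**Can the stated power be reproduced?** Not directly, because no SD is given. The SD that makes each statement an exact 80% point can be solved for:

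SD = d / [(1.960 + 0.842) × √(2/n)]

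- Protocol: 0.12 / (2.802 × √(2/61.2)) = 0.12 / (2.802 × 0.1808) = 0.237
- SAP: 0.16 / (2.802 × √(2/46.75)) = 0.16 / (2.802 × 0.2068) = 0.276

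Ignoring attrition in both, the SDs become 0.257 and 0.299, and the powers below do not change.

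**Does 0.12 become 0.16 when N falls from 432 to 330?** At a fixed SD, the detectable difference scales with 1/√N:

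0.12 × √(432/330) = 0.137

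Starting from 0.12, a threshold of 0.16 corresponds to N = 432 × (0.12/0.16)² = 243, or at N=330 to a variance (0.276/0.237)² ≈ 1.36 times as large. A Bonferroni correction over three strata would give 0.159, but the SAP states no such correction.

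**Within-BMI power at N=330** (46.75 per arm), from power = Φ(d / [SD × √(2/n)] - 1.960):

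| Difference (kg/week) | SD 0.276 (from the SAP's 0.16) | SD 0.237 (from the protocol's 0.12) |
|---|---|---|
| 0.16 | 80% | 90% |
| 0.145 (pilot, overweight) | 72% | 84% |
| 0.10 (pilot, obesity) | 42% | 53% |

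For example, at 0.10 with SD 0.276 the standard error is 0.276 × 0.2068 = 0.0571, and Φ(0.10/0.0571 - 1.960) = Φ(-0.21) = 42%.

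Over an assumed SD range of 0.20 to 0.35, power runs from 94% to 52% at 0.145 and from 68% to 28% at 0.10.

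**Overall power at N=330** (140.25 per arm), treating the outcome as weekly gain:

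| Difference (kg/week) | SD 0.276 | SD 0.237 |
|---|---|---|
| 0.16 | 99.8% | >99.9% |
| 0.145 | 99.3% | 99.9% |
| 0.1225 (mean of 0.145 and 0.10) | 96% | 99.1% |
| 0.10 | 86% | 94% |

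Power reaches 99% at a difference of about 0.141 (SD 0.276) or 0.121 (SD 0.237).

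**Number analysed.** SAP 4.2 drops participants inside the IOM range from the deviation analysis. As an illustration, with the overweight rates in SAP Table 1 (23.9% and 39.9% in range), 46.75 × 0.761 = 35.6 Usual Care and 46.75 × 0.601 = 28.1 SmartMoms participants remain. Power at 0.16 itself is then 63% (SD 0.276) or 76% (SD 0.237). The power text makes no allowance for this.

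**The case against.** The strongest reply is that both statements are open bounds. The SAP claims more than 80% power at 0.16 or above, which is true for any SD up to 0.276. The protocol's claim is true for any SD up to 0.237, and at 0.237 power at 0.16 is 90%. The two statements are therefore compatible. A reader might infer that one of them must be wrong, or that the trial cannot detect the pilot effect in obesity. The documents support neither: an SD of about 0.173 would satisfy both statements and give 80% power at 0.10. This stands, and it makes the powers above conditional. It does not supply the missing support: the protocol's wording presents 0.12 as a minimum, and nothing in either document shows 80% power at the pilot differences.

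A reader might also infer that the 99% claim is false. It is not shown to be. It agrees with the within-BMI statement at 0.16 (99.8%) and at 0.145 (99.3%). It concerns study observed GWG, which is analysed with a covariate-adjusted mixed model, so an unadjusted calculation on weekly rates cannot refute it.

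Other points stand in part:

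- The SAP does not literally claim 80% power at the pilot difference. The overstatement lies in the general wording of SAP 2.3 and 1.4.
- The amendment-log sentence about no new data comes from an entry on incidence rates, and the SAP redefines deviation as distance outside the range. Scaling to 0.137 assumes the same outcome and SD. If either changed, the SAP should say so.
- The obesity gap is not new: the protocol's 0.12 already exceeded 0.10.
- Weekly gain is a secondary endpoint in protocol 2.2, and SAP section 3 already urges caution with secondary results. That limits the harm but leaves the stated design property unsupported.

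**Conclusion.** The concern holds as a claim that the plan's own figures do not support, not as a proven error of arithmetic. The 0.16 kg/week threshold exceeds the pilot difference by 0.015 in overweight and by 0.06 in obesity. It also exceeds the rescaled protocol figure of 0.137 by 0.023.

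Read as 80% points, the stated differences imply power at the pilot effects of 72% to 84% in overweight and 42% to 53% in obesity. Obesity is the clearest case, since power falls short on either back-solved SD. These values rest on two-sided alpha of 0.05, 15% attrition, exact 80% points, and equating the pilot difference in deviation with the difference in weekly gain. A smaller true SD would raise them.

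The overall 99% statement is incomplete because it names no difference. It is consistent with the SAP's threshold at differences of about 0.14 kg/week or more.

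**What to change.** - In SAP 2.3.1, state the SD actually used for Hypothesis 2 and reconcile 0.12 at N=432 with 0.16 at N=330, naming any change of outcome or method behind it.
- Restate within-BMI power at the pilot differences of 0.145 and 0.10, on the number analysed for each outcome. The deviation analysis needs its own figure because in-range participants are excluded. If the SD cannot be recovered, give 72% and 42% (from 0.16) beside 84% and 53% (from 0.12) for weekly gain, labelled as conditional on back-solved SDs.
- Attach a difference to the 99% statement.
- In SAP 2.3 and 1.4, limit the within-BMI power wording for Hypothesis 2 to differences of 0.16 kg/week or more.

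The cost is SAP wording and less favourable stated figures. No extra participants and no change to the analysis are needed.
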